#### 3.2.1 Secondary objective endpoints

The secondary variables are:

- Mean change in tumor volume evaluated by pituitary MRI between baseline and weeks 4, 12, 24, 48, 72, and 96.
- Percent change in tumor volume evaluated by pituitary MRI between baseline and weeks 4, 12, 24, 48, 72, and 96.
- Proportion of patients reaching tumor volume decrease of at least  $\geq$  20% after 4, 12, 48, 72, and 96 weeks of treatment.

- Time to treatment response for treatment responders, defined as the time from the date of the first injection to the first evaluation in which the patient reached a tumor volume decrease of at least ≥ 20%.
- Change in grading score of disease-related symptoms between baseline and weeks 4, 12, 24, 48, 72, and 96.
- Incidence of pituitary hormone dysfunction at baseline and on weeks 4, 12, 24, 48, 72, and 96.
- Proportion of patients reaching alpha subunit decrease of at least 50% on weeks 4, 12, 24, 48, 72, and 96.
- Proportion of patients reaching alpha subunit normalization on weeks 4, 12, 24, 48, 72, and 96.
- Percentage of adverse events with CTC grade  $\geq 3$  during treatment with pasireotide LAR.
- Percentage of patients with at least one adverse event with CTC grade  $\geq 3$ .
- Incidence of all adverse events, incidence of abnormal lab values, and summary of laboratory evaluations.
- For the extension phase: among patients who had been considered as responders (i.e., patients reaching a tumor volume decrease of at least 20% compared to initial tumor volume), to evaluate the number and proportion of patients who remained responsive during the extension phase treatment (according to the magnetic resonance imaging evaluations on weeks 48, 72, and 96).
- To evaluate the percentage of patients remaining with stable tumor volume during the study, i.e., patients who mantained tumor volume variation lower than 20% compared to baseline tumor volume (according to magnetic resonance imaging evaluations on weeks 24, 48, 72, and 96).
- If applicable, to evaluate whether there was a difference in response among patients on 40 and 60 mg doses of pasireotide LAR.

# 4 Study design

A phase II, open-label, single-arm, prospective, multicenter study to evaluate the efficacy and safety of pasireotide LAR in adult patients with NFPA.

Eligible patients will receive 60 mg of pasireotide LAR every  $28 \pm 3$  days for 24 weeks, during the Main Phase of the study. The study is complemented by an extension. At the discretion of the treating physician, patients who benefit from the treatment with pasireotide LAR will be offered the opportunity to enter an Extension Phase, in which they will continue to receive pasireotide LAR 60 mg at 4-week intervals ( $\pm$  3 days) for up to 2 years (Table 7-2), or until pasireotide or other effective therapy is commercially available, or until clinical benefit is no longer seen (whichever occurs first). Dose decreases until 40 mg will be allowed, based on safety issues (see Section 6.4.2). In case of rapid deterioration of the visual field or sudden visual loss, the patient will be discontinued from the study.

During the Main Phase of the study, visits will be performed every  $28 \pm 3$  days. There will be two additional safety visits: Visit 3 and Visit 6.

The sella turcica MRI will be performed during the screening period (baseline imaging). The follow-up MRIs will be performed on weeks 4, 12, and 24 in the Main Phase and on weeks 48, 72, and 96 in the Extension Phase, and must be performed within 7 days of the appropriate visit. Enhancement with gadolinium contrast will be used to obtain the MRI.

The MRIs will be submitted to a central evaluator. In order to ensure consistency in all participating sites, MRIs must be performed and processed according to the guidelines of the central reading facility, which will be distributed to the sites before study start.

The visual field evaluations will be performed during the screening period (they will be considered as baseline data) and then every 4 weeks  $\pm$  3 days thereafter.

Symptoms and potential AEs will be evaluated on all visits. Safety-related tests will be performed as described on Table 7-1 and Table 7-2 (Visits and evaluations schedule for the Main Study).

Alpha subunit and pituitary hormone levels will be evaluated during the screening period (and will be considered as baseline data), as well as on Weeks 4, 12, and 24 in the Main Phase and on weeks 48, 72, and 96 in the Extension Phase.

The gallbladder ultrasound will be evaluated in the screening period and within 7 days of Visit 10 (Week 24). In the Extension Phase, it will be evaluated on weeks 48 and 96.

[figure not shown]
After the Main Phase of the study (first 24 weeks of treatment), patients deriving benefit from pasireotide LAR will be offered the opportunity to continue receiving pasireotide LAR, based on the physician's evaluation and the patient's wishes. This will be called study Extension Phase. The study design and a Main Phase and Extension Phase scheme are shown on Figure 4-1 and Figure 4-2, respectively.

Figure 4-1 Scheme of NFPA Study with Pasireotide LAR: Main Phase

Efficacy assessments: MRI, alpha subunit, symptoms

Special safety assessments: visual field \*, glycemia \*, ECG \*\* Efficacy Efficacy Efficacy Visit 3: Visit 6: safety safety Day -28 to Day -1 Visit 1 Visit 2: Visit 4: Visit 5: Visit 7: Visit 8: Visit 9: Visit 10: Visit 11: Injection 2 Injection 3 Injection 4 njection 5 Injection 6 Injection 7 follow-up 1 If the patient enters the extension phase, they will receive injection 7 Pasireotide LAR 60 mg im/28 days \* All visits, except 3 and 6

Figure 4-2 Scheme of NFPA Study with Pasireotide LAR: Extension Phase

\* For details of efficacy and safety evaluations, see Table 7-2.

\*\* All visits

# 5 Population

The population for this study consists of adults diagnosed with NFPA who did not receive any other previous therapy (treatment-naïve) for the disease. Due to the difficulty to evaluate changes in tumor volume in microadenomas, and also because they can be mistakenly diagnosed as incidentalomas, only patients with macroadenomas (≥ 1 cm) will be enrolled in the study. A total of 23 patients in 10 - 13 sites will be enrolled in this single-arm open-label study.

#### Inclusion / exclusion criteria

The investigator or his/her designee must ensure that enrollement in the study is offered to all patients meeting the inclusion and exclusion criteria.

#### 5.1 Inclusion criteria

- 1. Male or female patients  $\geq$  18 years old.
- 2. Patients with clinically non-functioning pituitary macroadenomas  $\geq 1$  cm.
- 3. Patients without previous treatment for NFPA.
- 4. Patients with Eastern Cooperative Oncology Group (ECOG) Performance status of 0 to 1.
- 5. Written Informed Consent Form obtained before any screening procedure.

#### 5.2 Exclusion criteria

- 1. Patients requiring surgical intervention for relief of any sign or symptom related to tumor compression.
- 2. Previous pituitary surgery.
- 3. Previous medical treatment for pituitary tumor.
- 4. Patients who received pituitary radiation within 10 years before the enrollment visit (Visit 2).
- 5. Prolactin (PRL) levels > 100 ng/mL. (PRL evaluation must be performed with diluted samples in order to ensure prevention of the "hook effect").
- 6. Patients with optic chiasm compression, causing clinically significant acute visual field defects.
- 7. Diabetic patients whose blood glucose is poorly controlled, as proven by HbA1C > 8%. Patients with known history of fasting glucose impairment or diabetes mellitus with HbA1c < 8% may be enrolled; however, blood glucose and antidiabetic treatment must be closely monitored throughout the study and adjusted as required.
- 8. Patients with known gallbladder or bile duct disease, or acute or chronic pancreatitis (patients with asymptomatic colelithiasis and asymptomatic dilation of the bile duct may be enrolled).
- 9. Patients with abnormal coagulation (increased PT or APTT 30% above normal limits) or patients who have received antiacoagulants that affect PT (prothrombin time) or APTT (activated partial thromboplastin time).
- 10. Patients with congestive heart failure (NYHA Class III or IV), unstable angina, persistent ventricular tachycardia, ventricular fibrillation, advanced cardiac block, or history of acute myocardial infarction within 24 weeks before the enrollment visit (Visit 2).
- 11. Screening (Visit 1) or baseline (pre-dose, Visit 2) QTcF > 450 msec.
- 12. Patients with history of syncope or family history of idiopathic sudden death.

- 13. Patients with persistent or clinically significant cardiac arrhythmias.
- 14. Patients with Torsades de Pointes risk factors, such as uncorrected hypocalemia, uncorrected hypomagnesemia, heart failure, clinically significant / symptomatic bradycardia, or high degree AV block.
- 15. Patients with concurrent disease(s) that might prolong the QT interval, such as autonomous neuropathy (caused by diabetes or Parkinson's disease), HIV, cirrhosis, uncontrolled hypothyroidism, or heart failure.
- 16. Patients on medication(s) known to prolong the QT interval.
- 17. Patients with liver disease or history of liver disease, such as cirrhosis, active chronic hepatitis B and C, or persistent chronic hepatitis, or patients with ALT and/or AST > 2 x ULN, total blood bilirubin > 1.5 x ULN, and serum albumin < 0.67 x LLN.
- 18. Patients with blood creatinine > 2.0 x ULN.
- 19. Patients with WBC  $< 3 \times 10^9 / L$ ; Hgb < 90% LLN; PLT  $< 100 \times 10^9 / L$ .
- 20. Patients with any current or previous medical condition that, in the investigator's opinion, might interfere in the study conduction or evaluation of the study results.
- 21. Patients with history of immunological impairment, including positive result for HIV tests (ELISA and Western blot). HIV tests will not be required; however, previous medical history will be analyzed.
- 22. Patients with known hypersensitivity to somatostatin analogues or any other pasireotide LAR compound.
- 23. Patients with active malignant disease within the last five years (except for basal cell carcinoma or in situ cervix carcinoma).
- 24. Patients with presence of uncontrolled, acute suspected, or active chronic infection.
- 25. Pregnant or breastfeeding patients, or patients of childbearing potential who do not adopt a clinically acceptable contraceptive method. If a woman is participating in the study, then one contraceptive method will be sufficient (pill or diaphragm), and the partner must use condoms. If an oral contraceptive is used in addition to condoms, the patient must have adopted this method at least two months prior to enrollment in the study, and must agree to continue to use it throughout the study, and for three months after the end of the study. Sexually active male patients are required to use condoms during the study and for three months after the end of the study, as a precautionary measure (the available data do not suggest any increase in reproductive risk with the study drugs).
- 26. Study participants on the investigational drug 30 days prior to the enrollment visit (Visit 2). Patients must have recovered from all side effects from other investigational therapies.

- 27. Patients with history of non-compliance to medical regimens, or patients considered potentially unsafe, or any circumstance at the time of study enrollment that might prevent the completion of the entire study or the follow-up required.
- 28. Patients with history or recurrence of undue use / abuse of alcohol or drugs within 12 months previous to visit 1 (screening).
- 29. Presence of Hepatitis B surface antigen (HBsAg).
- 30. Presence of Hepatitis C antibody screen (anti-HCV).
- 31. Patients who had a major surgery / surgical therapy for any cause within 4 weeks before randomization.
- 32. Patients with confirmed hypothyroidism, hypoadrenalism and hypogonadism (except for physiological andropause and menopause), unless appropriately treated with stable doses of hormone replacement therapy for at least 3 months before study entry.
- 33. Patients on growth hormone replacement therapy.
- 34. Patients with uncontrolled cardiovascular, renal or metabolic disorders.
- 35. Patients with severe neurological or psychiatric disorders.
- 36. Patients with contraindications to MRI such as, for example, (but not limited to): brain aneurysm clips, internal wiring of cardiac pacemaker and temporary pacemaker, cochlear implants, hearing devices containing internal non-removable parts, Swan-Ganz catheter, aortic balloon, Endovascular Graft Zenith AAA, and other potential contraindications related to ferromagnetic materials identified in the patient's interview.

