- Patients with known gallblader or bile duct disease, acute or chronic pancreatitis (patients with asymptomatic cholelithiasis and asymptomatic dilation of the bile duct may be enrolled)
- Patients with abnormal coagulation (increased PT or APTT 30% above normal limits) or patients who received anticoagulants affecting PT (prothrombin time) or APTT (active partial thromboplastin time)
- Patients experiencing congestive heart failure (NYHA Class III or IV), unstable angina, persistent ventricular tachycardia, ventricular fibrillation, advanced heart blockade, or history of acute myocardial infarction within 24 weeks previous to the enrollment visit (visit 2)
- Screening (Visit 1) or baseline (pre-dose, visit 2) QTcF > 450 msec
- Patients with history of syncope or family history of sudden idiopathic death
- Patients with persistent or clinically significant cardiac arrhythmias
- Patients with Torsades de Pointes risk factors, such as uncorrected hypopotassemia, uncorrected hypomagnesemia, heart failure, clinically significant / symptomatic bradycardia, or high degree AV block
- Patients with concurrent disease(s) that may prolong QT interval, such as autonomous neuropathy (caused by diabetes or Parkinson's disease), HIV, cirrhosis, uncontrolled hypothyroidism, or heart failure
- Patients taking medication(s) known to prolong QT interval
- Patients with liver disease or history of liver disease, such as cirrhosis, chronic active hepatitis B and C or persistent chronic hepatitis, or patients with ALT and/or AST > 2 x ULN, total blood bilirubin >1.5 x ULN, and blood albumin < 0.67 x LLN

- Patients with WBC count < 3x 10^9/L; Hgb < 90% LLN; platelets < 100x 10^9/l
- Patients with any current or previous medical condition that, in the investigator's opinion, may interfere with the conduction of the study or the evaluation of the study results
- Patients with history of immunological impairment, including a positive result for HIV tests (ELISA and Western blot). An HIV test will not be required; however, previous medical history will be analyzed
- Patients with known hypersensitivity to somatostatin analogues or any other pasireotide LAR component
- Patients with active malignant disease within the last five years (except for basal cell carcinoma or in situ cervix carcinoma)
- Patients with presence of uncontrolled, acute suspected, or active chronic infection

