# Visits and evaluations schedule

### Screening Visit:

Performed from Day -28 to Day -1 (Visit 1). Patients will receive the Informed Consent Form and, after signing it, they will be subjected to evaluations, including demographics, diagnosis and extent of disease, relevant / current medical history, verification of inclusion / exclusion criteria, vital signs, physical examination, ECOG performance status, ECG, blood pregnancy test, hematology and coagulation test, urinalysis, glucose and fasting blood insulin, HbA1c, chemistry, vitamin B12 and folic acid, hormone evaluation, alpha subunit evaluation, in visual field evaluation, gallblader ultrasound, pituitary / sella turcica MRI, and evaluation of concurrent medication and disease-related symptoms.

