This study has also shown that pasireotide LAR was generally well tolerated, and that the most common adverse events seen were gastrointestinal and mild in intensity. Although preclinical or clinical trials have not revealed any specific cardiac toxicity issue related to pasireotide, a complete clinical evaluation of QT/QTc was performed in healthy volunteers [CSOM230B2113]. In Part I of the study, 900 µg to 2100 µg doses of pasireotide were investigated, after which the maximum tolerated dose (MTD) of pasireotide was defined as 1950 µg SC BID. The MTD was then used as the pasireotide dose in Part II of the study (i.e., a 3-way crossover design using moxifloxacin, placebo and 1950 µg of SC pasireotide BID). The effect of pasireotide (at the MTD) on the QTcF interval was shown. This effect was based on the upper limit of the 1-sided 95% CI for the difference compared to placebo in QTcF

\*\* GH was collected at -30 and 0 min. (pre-dose). The mean of these first samples was calculated. The 4 remaining samples were collected post-dose and were not included in the mean calculation.

change from baseline of > 10 ms, in one or more timepoints. Pasireotide and moxifloxacin showed maximum effect 2 hours post-dose (QTcF change of 17.5 ms and 8.5 ms from baseline compared to placebo, respectively). Subjects receiving pasireotide also showed a HR decrease within 0 to 4 hours post-dose (maximum change versus baseline of 10.7 bpm). The appropriate monitoring of the ECG of patients assigned to pasireotide LAR arms is implemented in the protocol. Other detailed information on clinical efficacy and safety of pasireotide LAR may be found in the [Investigator's Brochure].

Study [CSOM230C2305] is evaluating the efficacy and safety of pasireotide LAR in patients with acromegaly (without medical treatment) compared to octreotide LAR. This study is still ongoing.

[figure not shown]
Other detailed information on clinical efficacy and safety of pasireotide LAR may be found in the [Investigator's Brochure].

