Blood pregnancy test 	Х							Х						X						Х	
Hematology (DB)	X							X						Х						Х	
Coagulation parameter PT	ΧE	хĸ	XK		XK	XK				Х	Х	Х	Х	Х		Х	Х	х	x	x	X
(D)	/\-	71.1	71.1	Χ	71.1	7111									X			~		_^_	^
Coagulation parameter	ΧE					Х				Х	Х	Х	Х	Х		Х	Х	х	х	x	
APTT (D)															X			~			
Urinalysis  (DB)	Х							Х						Х						Х	
Fasting blood glucose	Х							x						Ιx						x	
and insulin 2																					
HbA1c 	Х							Х						X						Х	
Chemistry 	Χ							Х						Х						Х	
LFTs (ALT, AST, total																					
bilirubin, albumin, ALP,	X			Х				Х						Х						Х	
γ-GT) (D)																					

Visit	10¹	11	12	402	13	14	15	16	17	18	19	20	21	22	23	24	25	26	27	28 EOS	29 Follow-up 
Week	24	28	32	35	36	40	44	48	52	56	60	64	68	72	76	80	84	88	92	96	Last dose + 8 weeks
Day	168	196	224	244	252	280	308	336	364	392	420	448	476	504	532	560	588	616	644	672	700
Injection	7	8	9		10	11	12	13	14	15	16	17	18	19	20	21	22	23	24		
Hormone evaluation  (DB)	Х							Х						Х						х	
Evaluation of the visual field 	Х							Х						Х						х	
Vitamin B12, folic acid 	Х							Х												Х	
Administration of Pasireotide LAR  (DB)	Х	Х	Х		Х	Х	Х	Х	Х	Х	Х	Х	Х	Х	Х	Х	Х	Х	Х		
Previous / concurrent medication  (DB)	Х	Х	Х	Х	Х	Х	Х	Х	Х	Х	Х	Х	Х	Х	Х	Х	Х	Х	Х		
Completion of the study  (DB)																					x

<sup>1 Patients who, according to the opinion of the physician in charge, are deriving benefit from pasireotide LAR treatment will be invited to participate in the extension phase.

<sup>2 Blood and urine must be collected before administration of the study drug. Patients must be fasting for 12 hours.

<sup>3 Hematology and coagulation include: hemoglobin, hematocrit (HCT), WBC count with differential, RBC count with differential, platelet count, PT, and APTT.

<sup>4 Complete chemistry includes: total bilirubin, total cholesterol, LDL, HDL, triglycerides, creatinine, urea, uric acid,  $\gamma$ -GT, total protein, albumin, SGOT, SGPT, CPK, LDH, alkaline phosphatase, sodium, potassium, inorganic phosphorus, chloride, and calcium. If total bilirubin concentration increases over 2.0 times the upper limit of normal, total bilirubin must be differentiated in direct and indirect reagent bilirubin.

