#### 7.5.6.3 Chemistry

A complete chemistry profile will be evaluated in the screening period and before administration of the study drug on each visit (except on Visit 2, Visit 3, Visit 6, and Visit 11, the Follow-up Visit) and will include: total cholesterol, low density lipoprotein (LDL) cholesterol, high density lipoprotein (HDL) cholesterol, triglycerides, calcium, phosphorus, chloride, sodium, potassium, inorganic phosphorus, creatinine, urea, uric acid, CPK, LDH, alkaline phosphatase,  $\gamma$ -GT, total protein, albumin, SGOT, SGPT, total bilirubin. In the Extension Phase, the chemistry profiles will be evaluated on visit 10 (Week 24) and then every 6 months thereafter (Weeks 48, 72, and 96).

[figure not shown]
If total bilirubin concentration increases more than 2.0 times the upper limit of normal, total bilirubin must be differentiated in direct and indirect reagent bilirubin on all visits.

Fasting blood glucose, insulin, and fasting chemistry evaluations will be performed in the screening phase and before administration of the study drug on each visit, except on Visit 2, Visit 3 (Week 3), Visit 6 (Week 11), and Visit 11 (Week 28, Follow-up Visit) in the Main Phase; they will also be performed on Weeks 48, 72, and 96 in the Extension Phase.

Liver function tests (ALT, AST, total bilirubin, albumin, ALP, and  $\gamma$ -GT) will be evaluated on visit 1 (screening), visit 2 (baseline), visit 6, and visit 10 for all patients. Liver function tests will also be evaluated on visit 3, visit 4, visit 401 (after 48 days), and visit 5.

HbA1c evaluations will be performed in the screening period (these will be considered as baseline data), on Weeks 12 and 24 in the Main Phase, and on weeks 48, 72, and 96 in the Extension Phase.

Vitamin B12 and folic acid evaluations will be performed in the Screening Period (these will be considered as baseline data), on Week 24 in the Main Phase, and on weeks 48 and 96 in the Extension Phase.

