3.1.2 Exclusion criteria

- 1. Patients who require a surgical intervention for relief of any sign or symptom associated with tumor compression.
- 2. Previous pituitary surgery.
- 3. Previous medical treatment for pituitary tumor.
- 4. Patients who have received pituitary irradiation within 10 years prior to inclusion visit (Visit 2).
- 5. Prolactin (PRL) levels > 100 ng/mL. (PRL evaluation should be performed with diluted samples to make sure to avoid the "hook effect.").
- 6. Patients with compression of the optic chiasm causing acute clinically significant visual field defects.
- 7. Diabetic patients whose blood glucose is poorly controlled as evidenced by HbA1C >8%. Diabetic patients whose blood glucose is poorly controlled as evidenced by HbA1C >8%. Patients with a known history of impaired fasting glucose or diabetes mellitus with HbA1c <8% may be included; however, blood glucose and anti diabetic treatment must be monitored closely throughout the trial and adjusted as necessary.
- 8. Patients with known disease of the bile duct or gallbladder, acute or chronic pancreatitis (patients with asymptomatic cholelithiasis and asymptomatic dilatation of the bile duct may be included).
- Patients with abnormal coagulation (PT and/or APTT elevated by 30% above normal limits) or patients receiving anticoagulants that affect PT (prothrombin time) or APTT (activated partial thromboplastin time).
- 10. Patients who have congestive heart failure (NYHA Class III or IV), unstable angina, sustained ventricular tachycardia, ventricular fibrillation, advanced heart block or a history of acute myocardial infarction within the 24 weeks preceding enrolment visit (Visit 2).

- 11. Screening (Visit 1) or baseline (predose, Visit 2) QTcF > 450 msec.
- 12. History of syncope or family history of idiopathic sudden death.
- 13. Sustained or clinically significant cardiac arrhythmias.
- 14. Risk factors for Torsades de Pointes such as uncorrected hypokalemia, uncorrected hypomagnesemia, cardiac failure, clinically significant/symptomatic bradycardia or high grade AV block.
- 15. Concomitant disease(s) that could prolong the QT interval such as autonomic neuropathy (caused by diabetes or Parkinson's disease), HIV, cirrhosis, uncontrolled hypothyroidism or cardiac failure.
- 16. Patients who are taking medication(s) known to increase the QT interval.

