 $^{^9}$ Complete biochemistry includes: total cholesterol, low density lipoprotein (LDL) cholesterol, high-density lipoprotein (HDL) cholesterol, triglycerides, calcium, phosphorus, chloride, sodium, potassium, inorganic phosphorus, creatinine, urea/BUN, uric acid, CPK, LDH, alkaline phosphatase, δ -GT, total protein, albumin, SGOT, SGPT, total bilirubin. If the total bilirubin concentration is increased above 2.0 times the upper normal limit, total bilirubin should be differentiated into the direct and indirect reacting bilirubin at visits.

Table A 2: Visit Schedule and assessments for extension study

Table A 2: Visit Schedule a	iiiu asses	3111611	13 101 6	EXCEIN	וטוו אנ	uuy															
Visit	10 ¹	11	12	402	13	14	15	16	17	18	19	20	21	22	23	24	25	26	27	28 TDE	29 FU ⁹
Week	24	28	32	35	36	40	44	48	52	56	60	64	68	72	76	80	84	88	92	96	Last dose + 8 weeks
Day	168	196	224	244	252	280	308	336	364	392	420	448	476	504	532	560	588	616	644	672	700
Injection	7	8	9		10	11	12	13	14	15	16	17	18	19	20	21	22	23	24		
Adverse events (D)	X	Х	Х	Х	Х	Х	Х	Х	Х	Х	Х	Х	Х	Х	Х	Х	Х	Х	Х	Х	х
Current medical conditions (D)	Х				Х			Х			Х			Х			Х			Х	х
Vital signs (D)	X				Х			Х			Х			Х			Х			Х	х
Physical exam (S)	Х				Х			Х			Х			Х			Х			Х	х
Weight (D)	Х				Х			Х			Х			Х			Х			Х	х
MRI / sella turcica	Х							Х						Х						Х	
Alpha subunit ²	Х							Х						Х						Х	
ECG (D)	Х				х			Х			Х			Х			Х			х	
Gallbladder ultrasound (D)	Х							Х												Х	
ECOG Performance status (D)	Х				Х			Х			Х			Х			Х			Х	х
Symptom assessment/ Disease related symptoms (D)	Х				Х			Х			Х			Х			Х			Х	
Serum pregnancy test ^{2,10}	Х							Х						Х						Х	
Hematology (D)	Х							Х						Х						Х	
Coagulation parameter PT (D)	XE	ХК	ХК	х	ХК	XK				Х	Х	Х	Х	Х	Х	Х	Х	Х	Х	Х	х
Coagulation parameter APTT (D)	XE					Х				Х	Х	Х	Х	Х	Х	Х	Х	Х	Х	Х	
Urinalysis ² (D)	Х							Х						Х						Х	

Fasting blood glucose and insulin ²	Х							Х						Х						Х	
HbA1c ²	х							Х						Х						Х	
Biochemestry ^{2,4}	Х							Х						Х						Х	
LFTs (ALT, AST, total bilirubin, albumin, ALP, γ-GT) (D)	Х			Х				Х						х						Х	
Hormonal evaluation ^{2,5} (D)	х							Х						Х						Х	
Visual field evaluation ⁶	Х							Х						Х						Х	
Vitamin B12, folic acid ²	Х							Х												Х	
Pariseotide LAR Admin ⁷ (D)	Х	Х	Х		Х	Х	Х	Х	Х	Х	Х	Х	Х	Х	Х	Х	Х	Х	Х		
Prior/Concomitant Meds ⁸ (D)	Х	Х	Х	Х	Х	Х	Х	Х	Х	Х	Х	Х	Х	Х	Х	Х	Х	Х	Х		
Study completition ⁹ (D)																					Х

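### Exclusion 14 names uncorrected hypomagnesemia, but no scheduled panel measures magnesium, so the criterion cannot be systematically verified from protocol-required data before the first depot injection.

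*Protocol*

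**What the plan says.** The criterion appears three times. Protocol section 5.2, criterion 14, includes "uncorrected hypomagnesemia, heart failure, clinically significant / symptomatic bradycardia, or high degree AV block". The synopsis has "Patients with Torsades de Pointes risk factors, such as uncorrected hypopotassemia, uncorrected hypomagnesemia, heart failure", and SAP section 3.1.2 has "Risk factors for Torsades de Pointes such as uncorrected hypokalemia, uncorrected hypomagnesemia, cardiac failure". Section 5.2 spells the companion electrolyte disorder as hypocalemia; the synopsis and SAP make clear that low potassium is meant.

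The synopsis list of screening tests includes "urinalysis, glucose and fasting blood insulin, HbA1c, chemistry, vitamin B12 and folic acid, hormone evaluation, alpha subunit evaluation", with no separate magnesium test. The chemistry panel is itemised in section 7.5.6.3 as "triglycerides, calcium, phosphorus, chloride, sodium, potassium, inorganic phosphorus, creatinine, urea, uric acid, CPK, LDH, alkaline phosphatase", with lipids before this run and protein and liver markers after it. Table 7-1 footnote 8 carries the same run. For the extension, Table 7-2 footnote 4 ends with "LDH, alkaline phosphatase, sodium, potassium, inorganic phosphorus, chloride, and calcium". The SAP schedule for the core study, Table A 1 footnote 9, has "triglycerides, calcium, phosphorus, chloride, sodium, potassium, inorganic phosphorus, creatinine, urea/BUN, uric acid, CPK, LDH, alkaline phosphatase". SAP Table A 2 footnote 4 gives a similar extension list. None of the five names magnesium.

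On QT risk, section 1.3.1 reports for pasireotide and moxifloxacin a "QTcF change of 17.5 ms and 8.5 ms from baseline compared to placebo, respectively". That result came from the subcutaneous form at its maximum tolerated dose in healthy volunteers.

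**The concern.** An eligibility rule that turns on a laboratory value needs a source for that value. Here the protocol names two electrolyte disorders in one criterion, schedules a test for one and not for the other. A site that follows the visit schedule exactly need never see a magnesium result.

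What is at stake is a safety screen. The first dose is a long-acting injection given on a 28-day cycle, which cannot be taken back once given. The protocol takes QT prolongation seriously enough to devote several exclusions and a cardiology pathway to it. A patient whom the protocol means to keep out could be enrolled with no protocol step having failed, and an auditor could not tell from the required data whether the criterion had been met.

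**Working it through.** No formula applies; the check is a reading of every laboratory list in both documents.

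**1. Is magnesium measured anywhere?**

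| Itemised chemistry list | Potassium | Magnesium |
|---|---|---|
| Protocol Table 7-1, footnote 8 | yes | no |
| Protocol section 7.5.6.3 | yes | no |
| Protocol Table 7-2, footnote 4 | yes | no |
| SAP Table A 1, footnote 9 | yes | no |
| SAP Table A 2, footnote 4 | yes | no |

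Potassium is in 5 of 5 lists, magnesium in 0 of 5. SAP Tables 27 and B 21 have rows for sodium, potassium, calcium, phosphorus and chloride, and none for magnesium. The hematology, coagulation, liver function, hormone, urinalysis and serology lists do not contain it either. Criterion 14 is the only place where magnesium status is mentioned.

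**2. Which sample would have to carry it?** Table 7-1 and section 7.5.6.3 schedule chemistry at screening (Day -28 to Day -1) and not at Visit 2, when the first injection is given. The screening sample is therefore the only full chemistry sample before exposure. The liver function tests drawn at Visit 2 include no electrolytes.

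**3. Does the protocol elsewhere rely on history for a laboratory-defined exclusion?** The exclusions for prolactin (5), HbA1c (7), PT and APTT (9), liver tests (17), creatinine (18), blood counts (19), HBsAg (29) and anti-HCV (30) each have a test on the screening schedule. HIV (21) does not, but that criterion says outright that no test is required and that medical history is used. Criterion 14 has neither a magnesium test nor such a statement.

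**4. What else stands between such a patient and the first dose?** QTcF above 450 msec at Visit 1 or pre-dose at Visit 2 (criterion 11), significant arrhythmia (13), the investigator's general discretion (20) and uncontrolled metabolic disorders (34). None of these requires a magnesium value.

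**The case against.** The strongest reply is that criterion 14 gives an illustrative list with no laboratory threshold, unlike criteria 17 to 19, and is meant for clinical judgement. Sites collect medical history, current conditions and concurrent medication at screening, may use any local result, and can exclude under criteria 20 or 34. Neighbouring criteria, such as syncope or family sudden death (12) and autonomic neuropathy (15), also rest on history without saying so. Section 9.1 requires monitors to verify inclusion and exclusion compliance in full.

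Much of this stands. A reader might infer that the criterion cannot be applied at all, or that sites will simply mark it as absent for everyone. The documents do not support that: known cases can be caught. But syncope or neuropathy can be established by history, whereas an unrecorded low magnesium can be found only by measuring it. Monitor verification does not help where no result is required.

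A reader might also infer that QT risk goes unscreened. It does not. Besides the QTcF entry limit, ECGs precede each Main Phase injection and are repeated on Days 20 and 76, and a QTcF above 480 msec leads to cardiology review (section 7.5.2.2). These are real but partial safeguards, since the protocol lists low magnesium as a risk factor separately from the QTcF limit.

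Finally, a reader might infer that a later QTcF rise could never be separated from an electrolyte cause. That goes too far. The cardiology work-up is open-ended, section 7.5.1 allows the nature of evaluations to change for an adverse event, and a screening value would not settle the cause of an event months later.

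**Conclusion.** The point holds as a mismatch between one stated eligibility criterion and the scheduled tests. The omission is certain: 0 of 5 chemistry lists and no SAP biochemistry row. Its consequence is limited to one layer of pre-dose safety screening, with other layers still in place. It does not affect the primary endpoint, its analysis or the sample size.

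The number of patients affected cannot be estimated. The documents give no prevalence of low magnesium, and any probability for the 23 enrolled patients would only restate an assumed prevalence, in a group already filtered by the other exclusions. The 17.5 ms figure shows why the protocol cares about QT risk; it is not an estimate for the depot, for which the documents give none.

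The conclusion assumes that local chemistry follows the protocol's itemised panel and that no site manual adds magnesium. The change is worth making because it is cheap and makes a stated safety rule auditable.

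**What to change.** Reconcile criterion 14 with the panel by adding serum magnesium to the Visit 1 chemistry sample, with the result available before the Visit 2 injection. Amend Table 7-1 footnote 8, section 7.5.6.3, SAP Table A 1 footnote 9 and SAP Table 27. In SAP Table A 1 the biochemistry row is marked 8 while the panel is itemised in footnote 9, so the marker should be checked at the same time.

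If magnesium is also kept at extension visits, amend Table 7-2 footnote 4, SAP Table A 2 footnote 4 and SAP Table B 21, so that the lists agree.

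If the sponsor does intend the criterion to rest on history, the minimum is to say so in criterion 14, as criterion 21 does for HIV. That makes the rule auditable but does not find an unrecorded case.

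The cost is one local-laboratory analyte on fasting blood already drawn, short wording changes in both documents, and possibly an occasional extra screen failure. No visit or blood draw is added. No saving should be claimed from the main-study panel's naming phosphorus twice: SAP Table 27 has a single phosphorus row, so a second assay that could be dropped is not shown.
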